9.2.1.3 Dexamethasone

Dexamethasone will be taken by mouth or by IV infusion once-daily on Days 1 (\pm 2), 8 (\pm 2), and 15 (\pm 2) for all cycles and on Day 22 (\pm 2) of Cycles 1 through 8. Dexamethasone will be administered at least 30 minutes (but no more than 4 hours) prior to carfilzomib. Subjects receiving dexamethasone IV on Days 1, 8, and 15 may receive dexamethasone orally on Day 22.

9.2.2 *CARFILZOMIB AND LENALIDOMIDE DOSE MODIFICATION GUIDELINES*

Dose reduction levels of carfilzomib and lenalidomide for toxicity management of individual subjects are provided in [Table 5](#) and [Table 6](#), respectively:

Table 5 Dose Decrement for Carfilzomib

Nominal Dose (mg/m ²)	Reduced Carfilzomib Doses (mg/m ²)		
	Dose -1	Dose -2	Dose -3
20	Discontinue		
56	45	36	Discontinue
70	56	45	36

Table 6 Dose Decrement for Lenalidomide

Nominal Dose (mg)	Reduced Lenalidomide Doses (mg)		
	Dose -1	Dose -2	Dose -3
25	15	10	5
10	5	Discontinue	—

Treatment guidelines for specific hematologic toxicities are outlined in [Section 9.2.2.1](#) and nonhematologic toxicities in [Section 9.2.2.2](#). In addition to dose reductions, administration of carfilzomib and/or lenalidomide may be held temporarily in the event of a treatment-related toxicity at the investigator's discretion. When administration of carfilzomib and/or lenalidomide is held, the reason must be documented in the case report form (CRF), and the medical monitor must be notified within 2 business days of the scheduled dose ([Section 9.1](#)).

If either the lenalidomide or carfilzomib dose level is reduced during a given cycle, the reduced dose level will be continued for the next cycle. If the reduced dose level is tolerated for a complete cycle, the subject may, at the investigator's discretion, resume the dose level prior to the reduction at the start of the subsequent cycle.

Carfilzomib or lenalidomide can be discontinued in the event of a treatment-related toxicity that, in the opinion of the investigator, warrants discontinuation. The subject will be considered still on protocol treatment as long as carfilzomib is being administered.

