9.2.2.3 Conditions Not Requiring Dose Reduction

The following conditions are exceptions to the above guidelines. Carfilzomib, lenalidomide, and dexamethasone do not need to be held in the following cases:

- Grade 3 nausea, vomiting, or diarrhea (unless persisting more than 3 days with adequate treatment of antiemetics or antidiarrheal agents)
- Grade 3 dexamethasone-related hyperglycemia
- Grade 3 fatigue (unless persisting for > 14 days)
- Alopecia

9.2.3 *DEXAMETHASONE DOSE MODIFICATION GUIDELINES*

Two dose reduction levels are defined for dexamethasone, as illustrated in [Table 10](#) below:

Table 10 Dose Decrments for Dexamethasone

Nominal Dose (mg)	Reduced Dexamethasone Doses (mg)	
	Dose -1	Dose -2
40	20	12

Dexamethasone will be permanently discontinued after 2 dose reductions in the event of additional dexamethasone-related toxicities. At the investigator's discretion, dexamethasone may be tapered prior to complete discontinuation according to institutional practice. The subject may continue on treatment with the other protocol-specified drug(s). Guidelines for dexamethasone dose modifications are summarized in [Table 11](#).

Table 11 Treatment Guidelines for Dexamethasone-related Toxicity

Dexamethasone-related Toxicities, All Days and Cycles		
Symptom	Findings	Recommended Action
Cardiovascular	Edema > Grade 3 (anasarca or limiting function and unresponsive to therapy)	
 Diuretics as needed, and restart dexamethasone at 1 dose decrement; if edema persists despite above measures, decrease dose by another dose decrement. Discontinue dexamethasone permanently if symptoms persist despite second reduction.
Gastrointestinal Toxicity	Dyspepsia, gastric or duodenal ulcer, or gastritis Grade 1 or 2 (requiring medical management)	
 Continue dexamethasone at same dose and treat with therapeutic doses of histamine 2 (H2) blockers, or proton pump inhibitor. Consider adding sucralfate or other antiulcer treatment as clinically indicated. If symptoms persist despite above measures, decrease dexamethasone dose by 1 dose level.

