2.1 Objectives and Endpoints

Objectives	Endpoints
Primary	

To evaluate the safety and tolerability of a once-weekly carfilzomib, lenalidomide, and dexamethasone (KRd) regimen in relapsed and refractory multiple myeloma (RRMM) and newly diagnosed multiple myeloma (NDMM) subjects	
Safety and tolerability of carfilzomib administered once weekly in combination with lenalidomide and dexamethasone, as defined by the type, incidence, and severity of Adverse Events (AEs) and changes from baseline in key laboratory analyses, including vital signs, and the extent and duration of exposure to study drugs
Secondary	

To evaluate the pharmacokinetics (PK) of carfilzomib when administered once weekly in a KRd regimen in RRMM and NDMM subjects separately.To evaluate the clinical activity (efficacy) of a once-weekly KRd regimen in RRMM and NDMM subjects separately	
Pharmacokinetics (PK) of carfilzomibOverall Response Rate (ORR), defined as the proportion of subjects who achieve a best overall response of stringent complete response (sCR), complete response (CR), very good partial response (VGPR), or partial response (PR) in accordance with IMWG-URC (Rajkumar et al. 2011)Complete Response Rate (CRR), defined as the proportion of subjects who achieve a best overall response of sCR or CR in accordance with IMWG-URCProgression-free Survival (PFS), defined as the time from the first day of study treatment to the earlier of disease progression or death due to any causeDuration of Response (DOR), defined as the time from the first evidence of confirmed PR or better to disease progression or death due to any cause among subjects who respond
Exploratory	

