For central laboratory FISH: Subjects with chromosomal abnormalities (CA) t (4;14) or t (14;16) in $\geq 10\%$ of screened plasma cells, and/or deletion 17p in $\geq 20\%$ of screened plasma cells are in high risk group. Subjects with other CA or normal cytogenetics are in standard risk group.

For local laboratory FISH (captured on eCRF): Subjects with chromosomal abnormalities (CA) t (4; 14) or t (14;16) and/or deletion 17p detected on FISH are in high risk group. Subjects with other CA or normal cytogenetics are in standard risk group.

Investigational Product (IP)

IP for this study refers to Kyprolis® (carfilzomib).

Informed Consent Date

The informed consent date is the date on which a subject signs the informed consent for this study.

International Staging System (ISS) Stage at Baseline

ISS stage at baseline will be calculated using serum beta-2 microglobulin and serum albumin value collected at baseline based on the criteria published by the International Myeloma Working Group ([Greipp 2005](#)).

ISS Stage I: Serum beta-2 microglobulin < 3.5 mg/L and serum albumin ≥ 3.5 g/dL

ISS Stage II: Serum beta-2 microglobulin < 3.5 mg/L and serum albumin < 3.5 g/dL or serum beta-2 microglobulin $3.5- < 5.5$ mg/L irrespective of the serum albumin

ISS Stage III: Serum beta-2 microglobulin ≥ 5.5 mg/L

Revised International Staging System (R-ISS) Stage at Baseline

R-ISS stage at baseline will be calculated using ISS (serum beta-2 microglobulin and serum albumin value collected at baseline, with ISS calculated as above), cytogenetic

risk group by FISH (central lab data, local lab data), and LDH, based on the criteria published by the International Myeloma Working Group ([Palumbo, 2015](#)):

R-ISS Stage I: Serum beta-2 microglobulin < 3.5 mg/L, serum albumin \geq 3.5 g/dL and standard risk CA by FISH and normal LDH

R-ISS Stage II: Not R-ISS I or III

R-ISS Stage III: ISS III and either high risk CA by FISH or greater than normal LDH

Last Dose Date

The last dose date is the date on which a subject is administered the final dose of any study drug.

Refractory to prior multiple myeloma therapy

Subject is refractory to a drug received in prior regimens if the data collected on prior multiple myeloma therapy CRF indicates that any of the following criteria is met:

- a. Best Response to any regimen containing the drug is stable disease or progressive disease
- b. Reason the drug was stopped is progression in any regimen

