9.6.1 Adverse Events and Disease-related Events

The Medical Dictionary for Regulatory Activities (MedDRA) version 21.0 or later will be used to code all adverse events (AEs) to a system organ class (SOC) and a preferred term (PT). The severity of AEs will be coded according to NCI-CTCAE v 4.03.

Treatment emergent adverse events will be summarized based on the number (%) of subjects experiencing events by MedDRA SOC and PT. The denominator for the percentage will be based on the number of subjects in the Safety Analysis Set.

Summaries of the subject incidence of the following TEAEs will be provided by SOC and/ or PT:

- All TEAEs
- TEAEs grade 3 or higher
- Fatal TEAEs
- Serious TEAEs
- TEAEs leading to withdrawal of carfilzomib
- Treatment-related TEAEs
- Treatment-related TEAEs grade 3 or higher
- **Treatment-related fatal TEAEs**
- **Treatment-related serious TEAEs**
- **Treatment-related TEAEs leading to withdrawal of carfilzomib**

Summaries that are displayed by SOC and PTs will be ordered by descending order of incidence of SOC and PT within each SOC for the total group. Summaries of TEAEs, and SAEs will be tabulated by SOC, PT and grade. Summaries of TEAEs, treatment-related AEs, and SAEs will also be provided by descending order of incidence of PTs in the total group

All TEAEs will be included in listings by subject. Listings of AEs determined to be DLTs, SAEs, AEs leading to discontinuation of study and AEs leading to discontinuation of investigational product will be provided.

A summary of the number of deaths and the cause of death, classified by deaths within 30 days of last dose of study drug and deaths more than 30 days after the last dose, will be provided.

Subject incidence of adverse events of interest (standardized MedDRA queries (**SMQ**) and/or Amgen MedDRA queries (**AMQ**)) will also be summarized according to their categories, PTs and grade. The adverse events of interest would include

- Acute renal failure (SMQ Narrow search)
- Cardiac arrhythmias (SMQ Narrow search)
- Cardiac failure (SMQ Narrow search)
- **Cardiomyopathy (SMQ Narrow search)**

- Dyspnoeas (HLT) - MedDRA Search Strategy HLT
- Embolic and thrombotic events, venous (SMQ Narrow search)
- Haematopoietic erythropenia (SMQ Broad search)
- Haematopoietic leukopenia (SMQ Narrow search)
- Haematopoietic thrombocytopenia (SMQ Narrow search)
- Haemorrhage terms (excl laboratory terms) (SMQ Narrow search)

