- Number (%) of subjects with doses missed, dose delays, dose changes, and dose interruptions for carfilzomib and dose changes and dose delays for lenalidomide and dexamethasone, respectively.

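### Withdrawal because of an AE is tabulated and listed for carfilzomib only, so AE-driven stopping of lenalidomide or dexamethasone alone goes unreported

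*SAP*

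**What the plan says.** The primary objective in SAP 2.1 concerns the three-drug regimen: "To evaluate the safety and tolerability of a once-weekly carfilzomib, lenalidomide, and dexamethasone (KRd) regimen". The matching endpoint is built from AEs, laboratory and vital-sign changes, and exposure to the study drugs. Withdrawal is not a named component.

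On AE-driven withdrawal, the plan contains the following:

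- SAP 9.6.1 has one all-cause table, "TEAEs leading to withdrawal of carfilzomib", and one related table, "Treatment-related TEAEs leading to withdrawal of carfilzomib".
- SAP 9.6.1 also states that listings of "AEs leading to discontinuation of investigational product will be provided". SAP Section 5 defines the investigational product as carfilzomib, so the listing has the same scope as the tables. A separate listing covers AEs that ended study participation altogether.
- SAP 9.2 summarises the main reason for stopping carfilzomib. It has no such line for the other two drugs.

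The protocol allows the drugs to be stopped separately. Section 9.2.2 says "Carfilzomib or lenalidomide can be discontinued in the event of a treatment-related toxicity" if the investigator judges this warranted, and counts the subject as on protocol treatment while carfilzomib continues. Section 9.2.3 ends dexamethasone permanently if dexamethasone-related toxicity continues after two reductions, and allows the remaining drugs to go on.

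For exposure, SAP 9.6.7 reports each drug's duration, cycles, subjects dosed per cycle, number of doses, cumulative dose and relative dose intensity. It adds "dose changes and dose delays for lenalidomide and dexamethasone, respectively".

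**The concern.** A reader of the study report will want to know how many subjects had to give up part of the regimen because of toxicity. The planned tables answer this for one drug of three. A subject who stops lenalidomide because of an AE and continues carfilzomib is in neither withdrawal table, nor in the investigational-product listing, nor in the SAP 9.2 reasons. The subject may also be absent from the SAP 9.2 count of subjects who discontinued treatment, because the protocol ties being on treatment to carfilzomib.

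The restriction is out of step with the rest of the safety plan. Protocol 5.2 counts a DLT if it is attributable to any of the three drugs, and SAP Section 5 starts the treatment-emergent window at the first dose of any study drug. Only the withdrawal analysis narrows to carfilzomib.

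**Working it through.** **Figure in the plan.** The documents state no withdrawal rate. Their one AE-incidence calculation (SAP 3.2: 38 subjects, 5% incidence, about 86%) reproduces as 1 − 0.95^38 = 0.858. It is not in dispute and does not bear on the gap.

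**Do other planned outputs close the gap?** Take a subject who stops lenalidomide alone because of an AE.

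- *TEAE tables and by-subject listing (SAP 9.6.1).* The AE is counted, also as grade 3 or higher, serious or related where it qualifies. That it ended a drug is not shown.
- *Regimen duration and cycles (SAP 9.6.7).* Duration runs to the last dose of all study drugs, and a cycle counts if any drug was given. Continued carfilzomib hides the stop.
- *Per-drug duration, cycles and subjects dosed per cycle (SAP 9.6.7).* The stop is visible as shorter lenalidomide exposure. The cause is not.
- *Lenalidomide dose changes and delays (SAP 9.6.7).* Neither is linked to an AE, and no discontinuation count is specified.
- *Relative dose intensity (SAP Appendix A).* Both numerator and denominator end at the drug's own last dose, so early stopping hardly registers.

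For the last item, suppose full lenalidomide through Cycle 2 Day 21 and then a permanent stop:

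- Cumulative dose, actual and planned: 2 × 21 × 25 mg = 1050 mg.
- Actual duration: last dose on study day 49, so (48 + 7)/7 = 7.857 weeks. Actual intensity: 1050/7.857 = 133.6 mg/week.
- Planned weeks: 4 + 4 = 8. Planned intensity: 1050/8 = 131.25 mg/week.
- Relative dose intensity: 133.6/131.25 = 102%.

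A subject who received lenalidomide in 2 of 18 possible cycles would show a relative dose intensity of 102%.

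**Size.** Let c be the proportion with AE-driven carfilzomib withdrawal, and w the proportion who stop lenalidomide or dexamethasone because of an AE without an AE-driven carfilzomib withdrawal. The any-drug proportion is c + w; the planned table gives c. Subjects who stop carfilzomib and a partner drug for the same AE are already in c. With group sizes from SAP 9.1 and w assumed:

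| Assumed w | Arm 3, n = 33 | RRMM 70 mg/m², n = 46 |
|---|---|---|
| 5% | 1.7 | 2.3 |
| 10% | 3.3 | 4.6 |
| 20% | 6.6 | 9.2 |

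Even at 5%, the chance that at least one such subject exists is 1 − 0.95^33 = 0.82 in Arm 3 and 1 − 0.95^46 = 0.91 in the RRMM group.

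**The case against.** The strongest reply is that little is hidden. The endpoint as worded is the safety and tolerability of carfilzomib given with the other two drugs, carfilzomib is the investigational product, and the protocol itself treats carfilzomib as the anchor of being on treatment. Protocol 13.5.2 asks for no withdrawal table at all, so the SAP already goes further than required. The rows are labelled for carfilzomib and will be right for carfilzomib. No hypothesis is tested, and dose-expansion decisions rest on DLTs from any of the three drugs and on the safety committee's review of all available data.

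Most of this stands. A reader might infer that subjects who stop a partner drug for toxicity drop out of the primary endpoint, or would pass as having tolerated the full regimen. The documents do not support either reading: the causal AEs enter the TEAE summaries, the shorter exposure enters the per-drug summaries, and both are named parts of the endpoint. Nor does the plan misstate a regimen-level withdrawal rate, because it promises none.

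What the reply does not supply is the link between the AE and the stopping of the partner drug. No planned summary makes it, and the objective asks about the regimen.

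**Conclusion.** The gap is real and limited. The planned outputs will not report how often an AE ended lenalidomide or dexamethasone alone, or which AEs were responsible. The carfilzomib row is a valid estimate for carfilzomib and a lower bound for AE-driven withdrawal from any component of KRd.

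The size cannot be taken from the documents. The figures of about 2–7 of 33 and 2–9 of 46 follow only from an assumed 5–20%, and the shortfall is zero if no subject stops a partner drug alone because of an AE. This is a reporting omission on the primary objective that should be repaired. It does not invalidate any planned analysis.

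**What to change.** In SAP 9.6.1 keep the carfilzomib rows. Add TEAEs leading to withdrawal of lenalidomide, of dexamethasone and of any study drug, each all-cause and treatment-related, and extend the discontinuation listing in the same way. In SAP 9.2 add the main reason for stopping lenalidomide and dexamethasone, where this is collected by drug.

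The cost is a few extra tables, with no new visits, subjects or design changes. It depends on the data being recorded by drug. Protocol 12.2.1.1 asks for relatedness to each study drug but lists action taken without saying that it is per drug. Protocol 9.2.2 requires the reason for a lenalidomide hold to be documented, while Protocol 11.1 asks for one primary reason for treatment discontinuation. The case report form should be checked first. If action taken is not held by drug, the SAP should say that the partner-drug rows cannot be produced.

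The carfilzomib rate will not change. The added any-drug rate can only equal or exceed it, and the report should present it as a separate quantity.

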9 DOSAGE AND TREATMENT ADMINISTRATION

9.1 TREATMENT REGIMEN

Carfilzomib, lenalidomide, and dexamethasone will be administered in 28-day cycles up to a total of 18 cycles. All cycles will start 28 days (\pm 2) after the start of the prior cycle. Cycle delays of more than 2 days must be discussed with the sponsor study medical monitor. All carfilzomib infusions and dexamethasone administrations will be within the 2 days of the scheduled administration unless approved by the sponsor study medical monitor.

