4.2 Subgroups

No subgroup analyses are planned in this study.

5. Definitions

Baseline

The baseline value is the closest recorded measurement prior to the first dose of study drug. If there are multiple valid records on an individual at the same date, then the record closest to cycle 1 day 1 will be used.

Best overall response by computational assessment

Best overall response will be derived using the Onyx Response Computational Assessment (ORCA) for multiple myeloma disease assessments based on the International Myeloma Working Group Uniform Response Criteria (IMWG-URC) ([Durie et al. 2006](#), with revisions, [Rajkumar, et al. 2011](#)). The detailed algorithm is documented in a separate document.

Best overall response by investigator assessment

Best overall response by investigator assessment is the best confirmed response by the analysis trigger date based on the responses by visit collected on myeloma response assessment CRF. The following confirmatory assessments are required for all response categories (sCR, CR, VGPR and PR) and PD:

- All laboratory-based progressive disease and all responses require two consecutive assessments made at any time before initiation of any new therapy. Confirmatory lab samples should be separated by at least one calendar day.
- Progressive disease by non-laboratory-based assessment (ie, plasmacytoma or skeletal lesion) does not require confirmatory report.
- All response categories also require no evidence of progression including new bone lesion, if radiographic studies are performed.
- Confirmation of CR or sCR requires local pathology review of a bone marrow biopsy or aspirate (a repeat confirmatory bone marrow sample is not required)
- Extramedullary plasmacytoma evaluation is required to confirm PR, CR, or sCR (if present at baseline)

Best overall response will be decided in the following order of confirmed responses: sCR, CR, VGPR, PR, SD, PD starting from the best to the worst.

End of Study Date for a Subject

The end of study date is the date recorded on the End of Study page for an enrolled subject.

First Dose Date

The first dose date is the date on which a subject is administered the first dose of any study drug.

Fluorescent in Situ Hybridization (FISH) Risk Group

Subjects in this study had FISH analysis performed by a central study laboratory and local laboratory.

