8.3 Handling of Missing and Incomplete Data

Missing and incomplete data will be identified through programmatic checks and a review of the tables and listings created within Biostatistics. Missing and incomplete data will be identified for investigation, and possible resolution, by DM and Global Study Management prior to each planned data snapshot and final database lock.

The handling of dropouts and missing disease status assessments for the efficacy variables is described in the description of the analyses. In general, data will be analyzed as retrieved from the study database and no imputation for missing data will be performed. Exceptions to this rule are detailed as below.

Missing or incomplete dates for adverse events, concomitant medications will be imputed as outlined by the algorithms below.

Table 3. Imputation Rules for Partial or Missing Start Dates

Start Date		Stop Date						
		Complete: yyyyymmdd		Partial: yyyyymm		Partial: yyyy		Missing
		< 1 st dose	≥ 1 st dose	< 1 st dose yyyymm	≥ 1 st dose yyyymm	< 1 st dose yyyy	≥ 1 st dose yyyy	
Partial: yyyymm	= 1 st dose yyyymm	2	1	2	1	n/a	1	1
	≠ 1 st dose yyyymm		2		2	2	2	2
Partial: yyyy	= 1 st dose yyyy	3	1	3	1	n/a	1	1
	≠ 1 st dose yyyy		3		3	3	3	3
Missing		4	1	4	1	4	1	1

1 = Impute the date of first dose

2 = Impute the first of the month

3 = Impute January 1st of the year

4 = Impute January 1st of the stop year

Note: If the start date imputation leads to a start date that is after the stop date, then do not impute the start date.

Imputation Rules for Partial or Missing Stop Dates

1. Initial imputation
 - If the month and year are present, impute the last day of that month
 - If only the year is present, impute December 31 of that year
 - If the stop date is entirely missing, assume the event or medication is ongoing
2. If the stop date imputation leads to a stop date that is after the death date, then impute the stop date as the death date.
3. If the stop date imputation leads to a stop date that is before the start date, then there is a data error and do not impute the stop date. (ie, set the stop date as missing).

If a partial or complete stop date is present and the 'ongoing' or 'continuing' box is checked, then it will be assumed that the adverse event or concomitant medication is ongoing. Missing stop dates will not be imputed beyond the subject last contact date or data cutoff date.

Imputation Rules for Partial or Missing Death Dates:

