- Hepatic failure, fibrosis and cirrhosis and other liver damage-related conditions (SMQ Narrow search)
- **Hepatitis B virus reactivation (AMQ including PTs: Hepatitis viral, Hepatitis acute, Hepatitis B, Acute hepatitis B, Hepatitis B reactivation, Hepatitis B DNA assay positive, Hepatitis B DNA increased)**
- Hypertension (SMQ Narrow search)
- Infusion reactions – (AMQ Narrow search)
 - event on same date of any Carfilzomib dosing
 - event on same date of first Carfilzomib dosing
- Interstitial lung disease (SMQ Narrow search)
- Ischaemic heart disease (SMQ Narrow search)
- Liver related investigations, signs and symptoms (SMQ Narrow search)
- Myocardial infarction (SMQ Narrow search)
- **Peripheral neuropathy (SMQ Narrow search)**
- **Progressive multifocal leukoencephalopathy (AMQ Narrow search)**
- Pulmonary hypertension (SMQ Narrow search)
- Respiratory failure (SMQ Narrow search)
- Respiratory tract infections (HLGT)
- Reversible posterior leukoencephalopathy syndrome (AMQ Narrow search)
- Torsade de pointes/QT prolongation (SMQ Narrow search)
- Tumour lysis syndrome (SMQ Narrow search)

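### Imputing an unknown AE start to the first-dose date can by itself make an infusion-reaction-term event count as a first-dose infusion reaction

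*SAP*

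**What the plan says.** SAP 9.6.1 lists infusion reactions among the adverse events of interest. They are identified by an AMQ narrow search and reported in two timing rows: "event on same date of any Carfilzomib dosing" and "event on same date of first Carfilzomib dosing".

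SAP 8.3 sets the date rule in general terms: "Missing or incomplete dates for adverse events, concomitant medications will be imputed as outlined by the algorithms below". In Table 3, code 1 reads "1 = Impute the date of first dose". The only stated exception for start dates is: "If the start date imputation leads to a start date that is after the stop date, then do not impute the start date".

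SAP section 5 defines the anchor by any of the three drugs: "The first dose date is the date on which a subject is administered the first dose of any study drug". Protocol 13.6 describes the imputation rules as conservative and leaves the detail to the SAP.

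**The concern.** Setting an unknown start to the first-dose date is a cautious choice for the treatment-emergent flag in SAP section 5, because the event is then kept in the safety tables. The infusion-reaction rows ask a different question. They use the date of onset as evidence of a link to a particular infusion, and for an imputed date that evidence has been supplied by the rule.

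At stake is the first-dose row, and its contrast with the any-dose row. Every subject receives 20 mg/m² on Cycle 1 Day 1 and the assigned dose of 56 or 70 mg/m² from Day 8. A Day 8 or Day 15 reaction recorded only by month, in the same month as first dose, would be tabulated against the 20 mg/m² infusion.

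**Working it through.** The plan states no figure on this point, so there is none to reproduce. The check traces the two rules and then sizes one affected subject.

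**1. When code 1 applies (SAP 8.3, Table 3).** It fills 12 cells, four in each of three rows:
- month and year known, equal to the first-dose month and year;
- only the year known, equal to the first-dose year;
- start wholly missing.

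In each row the four cells are a complete, month-year or year-only stop on or after first dose, and a missing stop.

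**2. Whether the stated exception helps.** It blocks an imputed start that is later than the stop. Under code 1 the imputed start is the first-dose date and the stop is on or after first dose or missing, so the exception is never triggered.

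**3. Test dates.** Assume a first dose on 10 March 2017 and a stop one day after true onset. Is the imputed start equal to the first-dose date?

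| True onset, days after first dose | Month and year known | Year only known | Start missing |
|---|---|---|---|
| 0, 7, 14 | yes | yes | yes |
| 28, 60, 200 | no | yes | yes |
| 490 | no | no | yes |

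**4. From first-dose date to carfilzomib date.** A yes in the table meets the first-dose row, and therefore the any-dose row, only if carfilzomib started on the first-dose date. The schedule intends this: all three drugs start on Cycle 1 Day 1, and Protocol 9.2.1.3 says "Dexamethasone will be administered at least 30 minutes (but no more than 4 hours) prior to carfilzomib". Protocol 9.1 allows some slack: "All carfilzomib infusions and dexamethasone administrations will be within the 2 days of the scheduled administration". If carfilzomib starts 2 days after another study drug, the imputed date does not match the first carfilzomib date.

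**5. Size.** SAP 9.6.1 reports subject incidence, so one additional subject adds 100/n points. Group sizes are from SAP 9.1.

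| Group | n | 100/n |
|---|---|---|
| Arm 1; Cohort 4 (each) | 9 | 11.1 |
| Cohort 1 | 10 | 10.0 |
| Cohort 2 | 12 | 8.3 |
| Arm 1 + Cohort 4 | 18 | 5.6 |
| Arm 3 | 33 | 3.0 |
| Arm 2 | 34 | 2.9 |
| Cohort 2 + Arm 2 | 46 | 2.2 |

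The number of AMQ-term events with missing or partial start dates is not in the documents, so the total effect cannot be computed.

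**The case against.** The strongest reply is that this will seldom happen and that little depends on it. Investigators must record onset dates (Protocol 12.2.1.1), and incomplete data are pursued before each snapshot and lock (SAP 8.3). Subjects are also watched on site for at least an hour after each Cycle 1 infusion (Protocol 9.2.1.1). Infusion reactions are one of 26 listed events of interest and are summarised descriptively with no hypothesis test. Dose decisions rest on DLTs and the safety committee's review, total TEAE incidence does not change, and every TEAE is listed by subject. All of this stands. It limits how often the problem arises and what follows from it, but it does not close the gap in the rule.

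A second reply is that dropping events with incomplete dates from a safety table is anti-conservative and could hide real reactions. That is a fair objection to simple exclusion. Reporting those cases separately meets it.

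Three stronger readings are tempting, and the documents do not support them:
- **Every AE of unknown onset becomes an infusion reaction.** The event must also be in the AMQ narrow search, and carfilzomib must have started on the first-dose date.
- **Each such AE adds one false case.** Incidence counts a subject once, so nothing is added if the subject already qualifies. The event may also have truly begun on the first-dose day, so the case is unsupported and not necessarily false.
- **Code 2 (first of the month) inflates the rows too.** With a stop on or after first dose, or missing, code 2 applies only outside the first-dose month, so it cannot create a first-dose case. For the any-dose row, the first of a month would fall on a dosing day with a chance of roughly 3/28, but so would a randomly timed true onset. No upward bias is shown.

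**Conclusion.** The point holds in limited form. Followed as written, the SAP can count an AMQ-term event of unknown onset as a first-dose, and hence any-dose, infusion reaction solely because of its imputed date. This rests on reading the general imputation rule in SAP 8.3 as feeding the date match. SAP 9.6.8 states a purpose for imputing medication dates, but nothing comparable confines AE imputation to the treatment-emergent flag. It also assumes that carfilzomib starts on the first-dose date, as scheduled.

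The ceiling is 1/n for each subject counted only through imputation, from 11.1 points in the groups of nine to 2.9 in Arm 2 among the individual cohorts and arms. The number of such subjects is unknown and probably small. The mechanism is clear from the text, but its effect on this study's results cannot be judged from the documents.

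**What to change.** In SAP 9.6.1, state that both same-date criteria use fully recorded, non-imputed AE start dates, matched to the actual carfilzomib dosing dates. Report the number of subjects with AMQ-term events of imputed onset in a separate row or footnote, so that no case is lost. Leave Table 3 unchanged for TEAE classification.

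The cost is one sentence in the SAP and one imputation-flag condition in the program, with no new data. The small downside is that a genuine same-day reaction with an incomplete date moves to the separate row.
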